Those randomized to the TIWeb or CSC intervention group will be told they will receive a TIWeb or CSC in the next week followed by data collection calls at four weeks and six months. Women randomized to the TIWeb plus CSC will be told they will receive access to TIWeb in the next week followed by the CSC about CRC or BC screening as well as data collection calls or electronic communication at 4 weeks and six months. The usual care group will be told they will receive telephone calls or electronic communication for data collection at 4 weeks and six months. At the 4-week interview, women will be queried about their receipt, recall, and use of the TIWeb and their recall of the CSC. At six months, women will be asked about their screening behaviors. Participants will be offered a \$20 gift certificate for each telephone survey they complete, for a total of \$60 per participant across the entire study. This small incentive compensates women for their time. **Table 1** contains a timeline of project activities.

D.6. Tailored Interactive Website (TIWeb).

The interactive program will operate from a computer. The specific

graphic design will be determined after Community Advisory Board (CAB) preference testing, but be similar to the sample screens provided in Appendix C. Control buttons will be large enough to be easily seen and will be clearly labeled for easy identification. The narrator will walk the viewer through every aspect of the program so that each woman can easily respond to data queries. The program will also be designed to allow a woman to stop the program at any given point and return later to that place in the program.

D.6.1. ITWeb Development:

Message libraries, tailoring algorithms, and the majority of the content that will be included in the proposed TIWeb and CSC have been

Figure 3. Flow of TIWeb Content for Group A (Non adherent to both CRC and BC)

[figure not shown]

Table 2. Messages for Screening by Stage

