The Center for Survey Research in Bloomington, by phone or electronically survey, will collect T1, T2, and T3 data and provide any technical assistance needed with the TIWeb. Participants who have questions about the TIWeb will be able to call a toll free number and a research assistant will call them back. The additional contact will be recorded for length of time and content and added as a covariate to final analysis. Extensive training will be required for all research assistants who collect data and provide technical help with the TIWeb. Research assistants who provide the CSC will be different individuals than those who do telephone interviews so that bias will not be introduced during data collection. Research assistants will be graduate students who will have an initial training session consisting of the following elements: 1) project rationale and overview, 2) detailed information about each intervention, 3) information about assisting women with the TIWeb, 4) delivery practice,

5) a detailed training manual, 6) an extensive question-and-answer period, and 7) breakout sessions for individualized role training. Although interviewers won't be blind to assignment, training will include extensive focus on standardizing the interviews.

D.10. Process Evaluation. Process evaluation for accrual will be determined by randomly selecting 25% of all accrual calls and rating callers using the evaluation checklist in **Appendix A**. Research assistants that receive below average on any criteria will be given additional training.

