site for other reasons. Therefore, use of self report in addition to claims data, and medical record audits will provide necessary outcome data. Participant involvement and beliefs will be assessed at 4 weeks post-intervention. As described previously, we may have women in the study who are at increased risk for CRC due to family history. For these women, colonoscopy is the most appropriate CRC screening test. However, some of these increased-risk women may decide to do FOBT instead of colonoscopy. In order to identify all behaviors, we will divide adherence to CRC screening into two categories-Risks Appropriate, and Any CRC screening after intervention. For most women who are at average risk, these classifications will be the same. However, for women with a family history of CRC, Risk-Appropriate CRC screening would be colonoscopy. **Table 6** defines each outcome. Data assessment times are specified in **Table 7**. Data collected for cost-effectiveness are described under the cost-effectiveness section.

Table 7: Data Assessment

Variable	Baseline	4 Weeks	6 Months
----------	----------	---------	----------

D.11. Measurement. Major outcome variables, delineated in Specific Aims, include: 1) Adherence and staging for CRC and BC, and 2) Cost-effectiveness.

The adherence to screening recommendations outcome will be assessed at 4 weeks and 6 months after intervention. As indicated in **Table 7**, the 4 week data collection will only be self report. Mammography and CRC screening and diagnostic tests at 6 months are the primary outcome and will include using claims data that identifies both screening and diagnostic codes in medical records as some test may be labeled diagnostic.

FOBT is not always charged to the patient. Therefore, verification of FOBT will require medical chart audit. A woman may not have a screening reported in her claims data because she is new to the health plan and received screening elsewhere. It is also possible that women may switch health plans or use another

Self Report CRCS and BCS	X	X	X
Screening Record verification	X		X
Knowledge and Beliefs	X	X	
Participant Involvement		X	
Demographic Variables	X		

Stage of Adoption for CRC and BC Screening:
Stage will be identified using measures of Prochaska and DiClemente's Transtheoretical Model developed for mammography by Rakowski and colleagues⁽¹¹⁹⁾,

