- **Missing data and methods for handling in analyses:** Missing data should be minimized by the use of telephone data collection and through interviewer training. Based on our previous work, we expect no more than 1-2% missing data for any single variable. Missing data for the major variables of CRC and breast cancer screening adherence (claims data) will be of concern if a woman changes health insurance plans. If a woman changes plans, we will still collect 6-month self-report data and inquire as to whether she has received either CRC or BC screening at another location. Because enrolled women will have signed informed consent to access claims data, we will be able to obtain CRC screening mammography records even in the event that health care plans have changed. We will examine reasons for drop-out and compare baseline characteristics of those with complete data versus those with missing data. If data are 'missing at random' (MAR) estimates will be biased and if 'missing completely at random' (MCAR) estimates will be inefficient if models are not adjusted for missingness. Therefore, we will use multiple imputation to perform adjustment for missingness. We will also perform sensitivity analyses to see how the results might have been affected under various assumptions had the data been available. The sensitivity analysis will also include estimating models while stratifying on the categories of missing data patterns,⁽¹⁴⁹⁾ although the multiple imputation method will be considered the more authoritative adjustment. Because patients will be randomized after they receive their baseline assessment, there are three possible missing data patterns (i.e., missing 2-week assessment, missing 6-month assessment, or missing both 2-week and 6-month). Furthermore, claims data will make it

possible to analyze adherence at 6 months even for women who dropped out, as long as claims data for those women can be obtained.

- **Sample bias:** We conservatively estimate that about 50% of contacted women will consent to participate, and women who are interested in CRC or BC screening may self-select into the study. Contacting only nonadherent women will minimize this bias.

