- **Feasibility/Clinical Relevance:** Either of the intervention strategies tested in the proposed project could easily be adapted into routine practice, if found effective. Previous studies have tailored interventions on a large number of variables necessitating lengthy interviews (Preliminary Studies). In contrast, the proposed interventions will be tailored on fewer variables and in an interactive format, thus facilitating data collection at baseline and “batch processing” the intervention. The TIWeb could even be distributed during routine care visits if a recent mammogram or CRC screening is not recorded on the chart. The addition of a CSC call from the provider’s office could also be incorporated into practice if found to have an additive value to the TIWeb.

E. Human Subjects

1. Risks to Subjects

Human Subjects Involvement and Characteristics. Participants in this study will be eligible if they have ever been a patient of any of the participating physicians; are age 50 to 75; are nonadherent to CRC or CRC and BC screening; and are able to complete telephone surveys and, depending on intervention, view a TIWeb, view a TIWeb and receive a counseling call, or receive usual care. Women will not be eligible if they have a history of adenomatous polyps, a personal history of CRC, inflammatory bowel disease or an hereditary syndrome (HNPCC\FAP). Eligibility criteria will be determined from both database records and self-report. Because this project involves mammography utilization, only women will be included.

Source of Materials: Data will be obtained from self-report at baseline and at 4-week and 6-month follow-up. Mammography status and CRC screening will be obtained from medical record data as well as self-report. Cost data will be obtained from the study administrative records.

Potential Risks: The proposed investigation does not present physical risk. Emotional or psychological risks, if they occur, would be slight. Possible fear or anxiety may be elicited when asking questions about BC,mammography, and/or colon cancer screening.

2. Adequacy of Protection against Risks

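### Six-month interviewers know the arm while self-report feeds the screening and stage outcomes, and no rule says when an unverified report counts

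*Combined protocol and SAP*

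**What the plan says.** **Interviewers.** D.9 says that although interviewers will not "be blind to assignment, training will include extensive focus on standardizing the interviews". It does separate roles: "Research assistants who provide the CSC will be different individuals than those who do telephone interviews". Under D.5, the telephone survey program shows the assignment to the research assistant once the baseline survey is complete. Under D.9, the survey center that collects data at all three time points also gives technical help with the website.

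**Screening outcome.** D.11 states: "Mammography and CRC screening and diagnostic tests at 6 months are the primary outcome and will include using claims data". It then explains that claims can miss tests, such as uncharged FOBT or tests done elsewhere, and concludes that "use of self report in addition to claims data, and medical record audits will provide necessary outcome data". Section E (Source of Materials) agrees: "Mammography status and CRC screening will be obtained from medical record data as well as self-report". For a woman who changes health plan, the missing-data paragraph after D.13 says "we will still collect 6-month self-report data and inquire as to whether she has received either CRC or BC screening at another location".

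**Stage outcome.** Hypothesis 1 also covers stage of adoption. Table 6 separates precontemplation from contemplation by whether the woman intends to be tested in the next six months. D.13 analyses advancement in stage from baseline to 6 months.

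**What is asked when.** D.5 puts the arm-specific items early: "At the 4-week interview, women will be queried about their receipt, recall, and use of the TIWeb and their recall of the CSC". For the final contact it says only: "At six months, women will be asked about their screening behaviors". Table 7 lists participant involvement at 4 weeks alone.

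**What is not said.** No section states which source prevails when self-report and records disagree, whether an unverified report counts as adherence, or whether those who code claims and charts know the arm.

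**The concern.** Participants know their arm, and women in the active arms have been urged to be screened. If they over-report tests, or if an interviewer who knows the arm probes differently, the error differs between active arms and usual care, and randomization does not remove it. The planned training and taping check consistency of delivery but leave the interviewer's knowledge of the arm in place.

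Two outcomes are exposed. For screening adherence, exposure depends on how often an unverified report settles a woman's status, and the plan sets no limit on that. For stage, a woman in precontemplation at baseline who says at 6 months that she intends to be tested counts as improved, and no record can confirm an intention.

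The missing source rule is a problem in its own right, since two analysts could code the same discordant woman differently.

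**Working it through.** **Inputs.** From D.12: 357 women per arm at 6 months; adherence of 20%, 30%, 40% and 55% in arms 1 to 4. D.12 states no significance level or sidedness; two-sided 0.05 is assumed.

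**Step 1: reproduce the plan's power.** With p̄ = (p1 + p2)/2, critical difference c = 1.96·√[2p̄(1−p̄)/n] and SE = √{[p1(1−p1) + p2(1−p2)]/n}, power = Φ[(|p1−p2| − c)/SE].

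- 20% vs 30%: c = 1.96·√(0.375/357) = 0.0635; SE = √(0.370/357) = 0.0322; power = Φ(1.133) = 0.871 (plan: .87).
- 30% vs 40%: c = 1.96·√(0.455/357) = 0.0700; SE = √(0.450/357) = 0.0355; power = Φ(0.846) = 0.801 (plan: .80).
- 40% vs 55%: 0.981 (plan: .98). The other three pairs exceed 0.99 (plan: .99).

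Also 397 × 0.90 = 357.3 and 4 × 397 = 1588. The assumed test therefore matches the plan's.

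**Step 2: effect of differential false reporting when nothing works.** The documents give neither of the two quantities that matter, so both are assumed:

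- f: excess proportion of unscreened active-arm women who falsely report a test (usual care set to zero);
- s: share of unscreened women classified by self-report alone.

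True adherence is 20% in both arms, so the observed active-arm rate is p2 = 0.20 + 0.80·f·s. The two-sided rejection rate is 1 − Φ[(c−d)/SE] + Φ[(−c−d)/SE], with d = p2 − 0.20.

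For f = 5% and s = 100%: p2 = 0.20 + 0.80 × 0.05 = 0.24; c = 1.96·√(0.3432/357) = 0.0608; SE = √(0.3424/357) = 0.0310; upper tail 1 − Φ(0.67) = 0.251; lower tail below 0.001; total 0.252.

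| f | s = 100% | s = 30% | s = 10% |
|---|---|---|---|
| 2% | 21.6% observed; 8.2% false positive | 20.5%; 5.3% | 20.2%; 5.0% |
| 5% | 24.0%; 25% | 21.2%; 6.8% | 20.4%; 5.2% |
| 10% | 28.0%; 71% | 22.4%; 12.3% | 20.8%; 5.8% |

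For a given f, the harm is governed almost entirely by s.

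**Step 3: is arm information needed at 6 months?** D.5 and Table 7 schedule receipt, recall, use and involvement at 4 weeks, and only screening behavior is described for the final survey. On that schedule nothing at 6 months calls for the arm. This is an inference, because the instruments are in appendices that are not shown. Table 7 is also incomplete: it omits stage, which D.13 analyses at 6 months.

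**The case against.** **The plan leans on records.** Table 7 schedules record verification at 6 months. D.11 requires chart audit to verify FOBT. The cost-effectiveness text names claims and medical records for the main outcome. The limitations text says adherence will be available through electronic records audit and expects records to be obtainable even after a change of plan. A reader might infer that a test counts on self-report alone. No section says so, and asking about tests elsewhere may serve only to trace records. This stands, and it narrows the point to an unstated rule.

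**Interviewer blinding does not reach the main mechanism.** A counselled woman who over-reports unprompted will do so to a blinded interviewer or on the electronic survey offered in D.1. This also stands; blinding removes only the interviewer's contribution. Hiding a field will not blind someone who gave the assignment, ran the 4-week interview or helped with the website.

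**Records-only might look like the obvious primary outcome.** The documents do not support making it so. D.11 adds self-report because claims miss real tests. Study staff schedule tests and mail kits for active-arm women (D.7, D.8), using a list of preferred sites (D.11), so those tests may be easier to find than usual-care tests done elsewhere. Nothing shows that tests would be missed equally across arms, and under-counting usual care would also favor the active arms.

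**The non-blinding is disclosed and mitigated** by separate counselling staff, standardized interviews and monthly taping. True, but none of these conceals the arm at 6 months.

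**Conclusion.** The concern holds in a limited form. Outcome interviewers know the arm, self-report contributes to the primary screening outcome, intention contributes to the 6-month stage outcome, and there is no source rule. Differential reporting or probing could therefore bias contrasts of the active arms with usual care.

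The size cannot be established. At an assumed 5% excess of false reports, the false-positive rate runs from about 25% (all unscreened women classified by self-report alone) to 6.8% (30%) and 5.2% (10%). These figures rest on zero false reporting in usual care, no true effect and a two-sided 0.05 test. They show sensitivity and are not evidence that such bias exists.

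A reader might infer that each point of false reporting adds a point to every effect, so that 5 points would be half of the planned 10-point contrast between usual care and arm 2. That would require every false report to count unverified, which the documents do not say. It also uses the smallest planned contrast with usual care: against the 20- and 35-point contrasts for arms 3 and 4, 5 points is 5/20 = 25% and 5/35 = 14%.

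The change is worth making because it is inexpensive, not because a large bias has been shown.

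**What to change.** 1. Hide the arm in the 6-month telephone module and from those who code claims and charts.
2. Where existing staffing allows, route each 6-month call to an interviewer who did not give that woman her assignment, her 4-week interview or website help. Put any question that could reveal the arm last.
3. Keep the combined-source primary outcome and state the source rule: which source prevails on disagreement, and whether and when an unverified report counts, applied identically in all arms.
4. Prespecify a sensitivity analysis that counts only tests verified in claims or chart audit.

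**Cost.** Survey programming, call routing and a few sentences of analysis text. If the assumed rates are kept, 397 per arm and the power table stand. The documents do not show whether full separation of 6-month interviewers would need more staff, so that step is conditional.

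**Downsides.** Blinding will be incomplete because women may reveal their arm, and it does not stop spontaneous over-reporting. The records-verified analysis may miss true tests done elsewhere, possibly unequally by arm, so it should be read beside the primary result and not as a replacement for it. Stated intention cannot be verified at all; for the stage outcome, blinding the interviewer is the only protection added here.
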